## Chronic Sleep Deprivation Among the Poor: A Lab-in-the-field Approach Statistical Analysis Plan

The purpose of this document is to outline the statistical analysis plan for analyzing all primary and secondary outcomes registered with clinicaltrials.gov collected for “Chronic Sleep Deprivation Among the Poor: A Lab-in-the-field Approach.”

The primary outcome is the amount of sleep per participant during each 24-hour period, measured in hours, which was collected using actigraphs.

The secondary outcomes include:

- Blood pressure, systolic, diastolic, pre-hypertensive, and hypertensive.
- Depression, measured by the PHQ-9 questionnaire
- Illness, defined as the number of days ill in the past week
- Inhibitory Control, measured by performance on a Hearts and Flowers test
- Memory, measured by performance on a Corsi memory test
- Attention, measured by performance on a Psychomotor Vigilance Task (PVT)
- Activities of Daily Living, measured by the SF-36 RAND health survey
- Subjective Well-being, measured using three questions from the Gallup survey
- Happiness, measured using two questions adapted from the SF-36 RAND survey and the Gallup poll

For all outcomes, the analysis consists of a regression to determine the effect of each of the five treatment arms, separately, on each outcome. The regression specification follows:

$$\gamma_{id} = \alpha + \beta_1 \cdot Nap + \beta_2 \cdot SleepDevices + \beta_3 \cdot DevicesIncentives + \beta_4 \cdot NapDevices \\ + \beta_5 \cdot NapDevicesIncentives + \delta_i + \varphi_i + \rho_d + \varepsilon_{id}$$

Where  $\gamma_{id}$  is each primary and secondary outcome for every participant  $i$  on day  $d$ .  $\alpha$  is the intercept.  $\beta_1$  to  $\beta_5$  capture the treatment effects, compared to the control group, of the nap only, sleep devices only, sleep devices and incentives, nap and sleep devices, and sleep devices, incentives, and nap treatment groups, respectively.  $\delta_i$  is the baseline measure of the dependent variable for participant  $i$ .  $\varphi_i$  is a vector of participant level controls, which include gender and age.  $\rho_d$  is a vector of day-level controls, including day in study fixed effects and calendar date fixed effects.

Each coefficient  $\beta$  represents the difference in the outcome variable, comparing each treatment arm to control, that is due to treatment. For each treatment group, the statistics reported are the mean of the control group summed with the respective coefficient, and the standard error of each coefficient estimated by the regression.

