Chronic Sleep Deprivation Among the Poor: A Lab-in-the-field Approach

NCT03322358

12/18/2018

Chronic Sleep Deprivation Among the Poor: A Lab-in-the-field Approach

Study Protocol

Overview. Given the potentially bidirectional relationship between sleep and the study's key outcomes of interest, and the potential for omitted factors influencing some or all of these variables, we will utilize a randomized-controlled trial (RCT) to provide rigorous identification. We will conduct the main study by recruiting approximately 450 participants to work full-time for up to 28 business days in a data-entry job. After an eight-day baseline period, participants are stratified into four cells by work productivity and sleep quantity (above vs. below median for both). Within each cell, participants are then randomized into the following three groups, with an equal number of participants in each group:

(1) *Control Group*: Participants in the control group continue to work in our lab office. They do not receive any of the below-mentioned sleep treatments, but they do receive placebo items so that any positive response from being able to take something home is similar across groups;

(2) *Night-Sleep Treatment*: Participants in the sleep treatment group receive sleep aid devices as well as feedback on their sleep, encouragement to sleep more if appropriate, and information regarding the benefits of sleep;

(3) *Night-Sleep Treatment + Incentives*: Participants in the sleep treatment + incentives group receive the same sleep aid devices, encouragement, and information as participants in the sleep treatment, but participants in the sleep + incentives treatment are also provided modest financial incentives according to how much they increased their sleep over the previous two nights compared to their average sleep during the baseline period.

Half of the participants across each of the three treatment groups will also be randomly assigned to take a half-hour nap each afternoon. The other half will be randomized into either taking a break or working during the same time slot. This results in six total experimental groups.

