(A) Sleep and sleep deprivation both constitute outcomes of interest of the study and serve as a “first stage” for the analysis of the impact of sleep on the remaining outcomes of interest. We will measure sleep and sleep deprivation via two objective and two subjective measurements. The primary measure of sleep relies on data from actigraphs, which resemble wristwatches and reliably and cost-effectively measure sleep/wake cycles via body movement. In addition, we will conduct a standard (in sleep medicine) psychomotor vigilance test (PC-PVT) on a daily basis, a reaction-time test used in sleep research as a proxy for sleep deprivation. These objective data will be complemented with self-reported sleep quantity and quality.

(B) Cognitive function is measured throughout the study period via a battery of laboratory tests conducted on a rotating basis. The tasks measure two key aspects of cognitive function, short-term memory (Corsi Block-tapping Task) and inhibitory control (Hearts and Flowers Task). The tasks are modified to cater to a low-literacy population.

(C) Health and subjective well-being. Happiness and life satisfaction reports will be elicited and anthropometric measurements taken at enrollment and exit. Additionally, participants will be asked to self-report health outcomes known to influence or be influenced by sleep including physical pain, hunger, mood, and stress. As sleep can also have an influence on self-control, we will track daily alcohol consumption through self-reports and objective measurements in the morning when participants arrive at the office. Finally, because sleep restriction has been shown to affect cardiovascular function, we will collect blood pressure readings multiple times.

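### The hypertensive and pre-hypertensive models adjust for baseline category but not for continuous baseline systolic and diastolic pressure, giving up a little precision on two secondary outcomes

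*SAP*

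**What the plan says.** The SAP's list of secondary outcomes has a single blood-pressure entry: "Blood pressure, systolic, diastolic, pre-hypertensive, and hypertensive". That is two continuous measures and two categories, and the cut-offs are not defined.

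The regression specification is common to everything: "For all outcomes, the analysis consists of a regression to determine the effect of each of the five treatment arms". In it, δ_i "is the baseline measure of the dependent variable for participant" *i*. The participant-level controls named beside it are gender and age. The day-level controls are fixed effects for day in study and calendar date. Nothing in the SAP brings baseline systolic or diastolic pressure into the two category models.

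The protocol, Outcomes item (C), says "we will collect blood pressure readings multiple times" but gives neither the number of readings nor their days. A continuous baseline is implied by the SAP, because the systolic and diastolic models need one as their own δ_i.

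**The concern.** A category indicator gives a participant just below the cut-off the same baseline value as one far below it, although their chances of being above it later differ. The readings behind the indicator carry that information. Leaving them out makes the residual variance larger than it needs to be, and with it the standard error of each treatment coefficient.

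Randomisation does not make up for this. The protocol's Overview stratifies on work productivity and sleep quantity, not on blood pressure, so covariate adjustment is the only control for chance differences in baseline pressure. Each coefficient compares one cell of the six-group design with control, so the category outcomes are imprecise to begin with.

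**Working it through.** The documents give no prevalence, correlation, standard deviation, power or sample-size figure for blood pressure, so there is no planned figure to reproduce.

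**Inputs from the documents.** The protocol's Overview plans "recruiting approximately 450 participants to work full-time", three night-sleep groups "with an equal number of participants in each group", and a nap split within each: "Half of the participants across each of the three treatment groups will also be randomly assigned". It adds: "This results in six total experimental groups". Hence 450/6 = 75 per cell.

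**Assumptions.** Baseline and follow-up pressure are bivariate normal with correlation r of 0.5 to 0.8. Hypertensive prevalence p is 10% to 40%. There is one follow-up reading per person, and the model is linear, as in the SAP's equation. For the detectable difference, two-sided 5% and 80% power are assumed (multiplier 1.960 + 0.842 = 2.802).

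**Formulae.**
- SE of one arm against control = √[p(1−p)(1−R²)·2/75]
- SE ratio = √[(1−R² with flag and continuous value)/(1−R² with flag only)]. This does not depend on the 75.
- Sample-size equivalent = 1 − (SE ratio)²

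**Worked case, r = 0.6, p = 0.2.** Simulation gives R² = 0.137 with the flag and 0.188 with both.
- Flag only: √[0.16 × 0.863 × 2/75] = 0.0607; detectable difference 2.802 × 0.0607 = 17.0 points.
- Flag plus continuous: √[0.16 × 0.812 × 2/75] = 0.0589; detectable difference 2.802 × 0.0589 = 16.5 points.
- SE ratio 0.970, a cut of 3.0%, worth about 6% of the sample.

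**Hypertensive, range (before age and gender).**

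| r | p | R², flag | R², flag + continuous | SE ratio | SE cut |
|---|---|---|---|---|---|
| 0.5 | 10% | 0.062 | 0.096 | 0.982 | 1.8% |
| 0.5 | 40% | 0.109 | 0.156 | 0.973 | 2.7% |
| 0.6 | 20% | 0.137 | 0.188 | 0.970 | 3.0% |
| 0.8 | 10% | 0.263 | 0.306 | 0.971 | 2.9% |
| 0.8 | 40% | 0.346 | 0.420 | 0.941 | 5.9% |

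The extremes are worth 1 − 0.982² = 3.6% and 1 − 0.941² = 11.4% of the sample.

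**Allowing for age and gender.** If these explain 20% of blood-pressure variance (assumed), the cut over the same range is 0.7% to 4.6%. At 30% it is 0.3% to 3.8%. A repeat simulation gave the same figures.

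**Other forms of the baseline (before age and gender).**
- With separate systolic and diastolic values and an either-above-threshold rule (r 0.5 to 0.8), the cut is 2.3% to 5.4%.
- If the baseline is the share of 2 or 3 readings above the cut-off (r 0.6 to 0.7, p = 0.2), the cut is 2.0% to 2.7%.

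**Pre-hypertensive (before age and gender).**
- As a middle band (prevalence 30% to 40%, r 0.4 to 0.8), adding a linear term cuts the SE by 0% to 2.0% and a flexible term by 0.3% to 3.9%. The zero arises for a central band, where the relation to baseline rises and then falls.
- If the category means at or above the lower cut-off (r 0.5 to 0.8), the ratios of 0.9393 to 0.9746 give cuts of 2.5% to 6.1%.

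**Replacing the flag with a linear term.** At r = 0.8, p = 10% for hypertensive, R² falls from 0.263 to 0.219. Residual variance is then 0.781/0.737 = 1.06 times as large, and the SE rises by about 3%. For a central 40% band at r = 0.8 the SE rises by 5.0%.

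**The case against.** The best case for the plan as written has four parts.

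First, the efficient blood-pressure analysis is already there. Systolic and diastolic pressure are outcomes in their own right with their own continuous baselines, so the information is not lost to the trial. That is true, but it does not sharpen the two category analyses, which the SAP also reports.

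Second, one specification for all outcomes limits outcome-by-outcome discretion. That is a fair reason for the choice. A covariate rule written into the SAP in advance keeps the same protection.

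Third, the gain is small and uncertain. This stands. In the worked case the detectable difference moves by half a point, age and gender may already recover part of the gain, and prevalence and correlation are both assumed. That the baseline is a yes/no flag is also inferred from the definition of δ_i. If several readings are averaged into a share, the gain shrinks but remains.

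Fourth, a careless remedy can do harm. This stands too: putting linear terms in place of the flag can raise the standard error.

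A reader might infer that the flag-only model biases the treatment effects, or that continuous baselines would narrow every coefficient at no cost. Neither is supported. Treatment is randomised, so the flag-only contrast is unbiased. The documents do not define the pre-hypertensive category, and if it is a central band a linear term adds nothing. The extra terms also use degrees of freedom.

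**Conclusion.** The point holds as a minor matter of efficiency on two secondary outcomes. The hypertensive and pre-hypertensive models use baseline category, gender and age, and leave out continuous baseline pressures that the plan's own systolic and diastolic models require. There is no bias, and the primary sleep outcome is unaffected.

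Hypertensive status is the firmer case. In every hypertensive scenario examined, adding the continuous value to the flag lowered the standard error. The range runs from about 0.3%, with low correlation, low prevalence and strong age and gender effects, to about 6% with high correlation, 40% prevalence and no help from age and gender. For pre-hypertensive the size depends on a definition that the documents do not give. All of these figures rest on assumed prevalence, correlation and normality. No conclusion of the trial is likely to turn on them.

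**What to change.** Add one sentence to the SAP's regression specification: for the pre-hypertensive and hypertensive outcomes, mean baseline systolic and mean baseline diastolic pressure enter as continuous covariates, preferably in flexible form such as a quadratic or spline, in addition to the baseline category indicator. Do not drop the indicator. In the same place, define the two categories and state which readings form the baseline, since the form of the covariate depends on both.

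In the linear model the treatment contrast being estimated stays the same, because the added covariates are measured before randomisation. No new data are needed. The cost is a few degrees of freedom among about 450 participants. If these outcomes have already been analysed, keep the specified analysis and report the adjusted one as supplementary.

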Sleep will be objectively measured using wristwatch-like actigraphs, which accurately infer sleep from movement. In order to estimate the labor market effects of improved sleep, productivity, labor supply, and earnings will be measured using performance on the data-entry task. Variations on the data-entry task and a savings activity will be used to understand effects on economic decision-making, as measured by intertemporal choices and reaction to the salience of work incentives. All participants will also engage in standard lab tests of aspects of cognitive function as well as surveys and measurements of health.

Sample. All participants will be low-income residents of Chennai, India. Given the importance of sleep to all genders, we will enroll both men and women.

Process and timeline. During their participation in the study, individuals will attend the study office six days per week for 6 to 10 hours per day. During each of their visits, individuals will primarily work on a data-entry task, which will create precise measures of their labor supply and productivity, but will also complete a brief daily survey to assess self-reported sleep and covariates of interest (e.g. caffeine intake), undertake a battery of cognitive tasks, and make a daily decision whether to save money at the office at a favorable interest rate. More extensive surveys are also taken at enrollment and endline and additional health measures are collected as described below. All participants will follow a thorough informed consent procedure prior to enrollment.

Baseline period. The experiment will begin with an eight-day baseline period without any experimental variation. This baseline period serves two main goals. First, it will generate baseline

information on key covariates, which will allow us to stratify treatment conditions based on baseline outcomes, boosting statistical power and reducing the danger of baseline imbalances across treatment groups along key dimensions. Second, it ensures a population with sufficiently high attendance, promoting internal validity, since only participants who complete the baseline period are entered into the main study.

Treatment conditions. Upon completion of the baseline period, experimental variation in sleep is created in two ways: (1) two interventions to improve individuals' home sleep environments and attitudes towards sleep (randomized across individuals), and (2) a napping intervention (randomized across individuals).

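### The SAP regression does not name the four randomisation cells among its controls; adding them, together with participant-clustered standard errors, is a minor and nearly free refinement

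*SAP*

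**What the plan says.** **Design (Protocol, Overview).** After the baseline period, "participants are stratified into four cells by work productivity and sleep quantity (above vs. below median for both". The text continues: "Within each cell, participants are then randomized into the following three groups, with an equal number of participants in each group". Nap is described separately: "Half of the participants across each of the three treatment groups will also be randomly assigned to take a half-hour nap each afternoon". That sentence does not say whether nap was assigned within the cells. The trial plans on "recruiting approximately 450 participants to work full-time for up to 28 business days in a data-entry job", of which eight are baseline.

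**Purpose (Protocol, Baseline period).** Stratifying on baseline data is meant for "boosting statistical power and reducing the danger of baseline imbalances across treatment groups along key dimensions".

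**Analysis (SAP, regression specification).** One participant-by-day model serves all primary and secondary outcomes. It has five arm indicators, the baseline value of the outcome, a participant-level term that "is a vector of participant level controls, which include gender and age", and study-day and calendar-date fixed effects. The cells are not named, and neither is baseline productivity. Baseline sleep enters only where sleep is the outcome. The reported standard error is the one the regression produces; no clustering is stated.

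**Timing of outcomes (Protocol, Outcomes A and C).** Some outcomes are repeated, for example a "psychomotor vigilance test (PC-PVT) on a daily basis". Others have one follow-up value: "Happiness and life satisfaction reports will be elicited and anthropometric measurements taken at enrollment and exit".

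**The concern.** An analysis normally carries the factors used to restrict the randomisation. If a factor is balanced by design and predicts the outcome but is left out of the model, its between-cell variance stays in the residual. The model-based standard error then ignores balance that the design has already achieved, and is somewhat too large relative to the true spread of the estimate.

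At stake are slightly wider intervals than the design warrants and, if nap was not assigned within the cells, a small loss of true precision on some contrasts. For sleep, only productivity is missing, because baseline sleep is already a covariate. For most secondary outcomes, such as blood pressure and PHQ-9, neither stratifier is named. Productivity as an outcome lies outside this SAP (Protocol, closing note), but baseline productivity is still a randomisation factor for every outcome within it.

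**Working it through.** The plan states no power, SD, intraclass correlation (ICC) or covariate correlation, so there is no figure of its own to reproduce.

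**Inputs from the documents.** N about 450, so 150 per night-sleep group and 75 per arm. Four cells, hence three dummies. Post-baseline days: 28 − 8 = 20.

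**Assumptions.** Each stratifier has correlation r with the participant's mean outcome after the SAP covariates, with r from 0 to 0.3. Stratifiers are roughly normal and independent of each other. The number of new stratifiers k is 1 for sleep and 2 for secondary outcomes.

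**Step 1: participant-level or clustered SE.** A median split keeps 2/π of a normal covariate's explained variance, so R² = k(2/π)r² and the SE falls by 1 − √(1 − R²). The cost of three more parameters is about √(441/438) − 1 = 0.3% (N less 9 or 12 coefficients).

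| r | R², k=1 | SE fall, before / after cost | R², k=2 | SE fall, before / after cost |
|---|---|---|---|---|
| 0 | 0 | 0 / rise of 0.3% | 0 | 0 / rise of 0.3% |
| 0.1 | 0.0064 | 0.3% / 0.0% | 0.0127 | 0.6% / 0.3% |
| 0.2 | 0.0255 | 1.3% / 0.9% | 0.0509 | 2.6% / 2.3% |
| 0.3 | 0.0573 | 2.9% / 2.6% | 0.1146 | 5.9% / 5.6% |

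Simulation with one value per participant at r = 0.3 gave falls of 2.8 to 2.9% (primary) and 5.7 to 6.0% (secondary). If the two stratifiers correlate 0.3 or 0.5 with each other, the 5.9% becomes 4.9% or 4.4%.

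**Step 2: does the true spread change?** This depends on how nap was assigned.

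- *Nap within cells.* All six arms are balanced on the cells by design. In simulation at r = 0.3 (20 days, ICC 0.3) the true SD of the estimates was the same with and without the dummies: 0.0921 (primary) and 0.0881 (secondary). The clustered SE went from 0.0938 to 0.0908 and from 0.0941 to 0.0882, so the dummies bring a conservative SE down to the true spread.
- *Nap not within cells.* The three groups are balanced, but the halves within a group need not be. Drawing 75 of 150 leaves half the usual sampling variance of an arm's cell mix. The four contrasts that cross night-sleep groups therefore carry R²/2 of excess variance, and nap-only against control carries all of R². At r = 0.3 the cross-group fall is 1 − √[(1 − R²)/(1 − R²/2)] = 1.5% (k=1) or 3.1% (k=2). Averaged over five contrasts this is (2.9 + 4 × 1.5)/5 = 1.8% and (5.9 + 4 × 3.1)/5 = 3.7%, before the small parameter cost. Simulation agreed: 0.0937 to 0.0923 (1.5%) and 0.0921 to 0.0887 (3.7%).

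**Step 3: unclustered participant-day SE.** The fall is 1 − √{1 − R²[ICC + (1 − ICC)/20]}. At r = 0.3 and assumed ICC 0.1, 0.3 and 0.5 it is 0.4%, 1.0% and 1.5% (primary), and 0.8%, 1.9% and 3.1% (secondary). At ICC 0.3 and r = 0.3 with nap within cells, the primary true SD is 0.0921 against a reported SE of 0.0365, a ratio of 2.5. Adding the dummies lowers that SE to 0.0361 and leaves the true SD where it was.

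**The case against.** The strongest case against has four parts.

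- *The list is open.* The SAP says which controls are included, not that there are no others. This stands as far as it goes: the point is only that the cells are not named.
- *The size is assumed.* This stands. The 6% end needs two independent stratifiers, each correlated 0.3 with the outcome after its own baseline, gender and age. Nothing in the documents supports or excludes that for blood pressure or PHQ-9, and zero is within the range.
- *There may be no true gain.* This also stands in part. A reader might infer that leaving out the cells forfeits the power for which the protocol stratified. If nap was assigned within the cells, that is wrong, because the balance has delivered the precision already. The protocol leans that way without settling it: its Baseline period paragraph speaks generally of stratifying treatment conditions, and the next paragraph counts nap among them.
- *Clustering matters far more.* This stands, and it limits the remedy. On unclustered participant-day data, the dummies alone would shrink a standard error that is already far too small. The participant-level figures do apply without clustering to happiness and life satisfaction, which have one follow-up value.

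What survives is a documented randomisation factor that the single model does not name, and a change that needs no new data.

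**Conclusion.** The omission is real and minor. For participant-level or participant-clustered standard errors, adding the cells gives anything from a rise of at most about 0.3% to a fall of about 3% (primary) or 6% (secondary), under assumed correlations of 0 to 0.3. Whether that is a gain in true precision or only a more accurate reported standard error depends on the nap assignment, which the documents leave unstated.

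Two stronger readings should be resisted. The treatment effects are not biased, since allocation is random whether or not the cells are modelled. Nor does leaving out the cells make the standard errors too small; taken alone, it makes them slightly too large if anything. Any understatement would come from unclustered participant-day errors (a factor of about 2.5 at an assumed ICC of 0.3 over 20 days), which is a separate and larger matter.

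**What to change.** In the SAP regression specification, extend the participant-level controls for all outcomes to gender, age and indicators for the four randomisation cells (baseline productivity above or below median by baseline sleep above or below median; three dummies). In the same amendment, specify standard errors clustered by participant for every outcome measured on more than one post-baseline day. The dummies should not be added without this. State also whether nap was assigned within the cells.

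The SAP refers to the actigraph data in the past tense. If outcome data were in hand when the change is made, label it as an amendment and report each model with and without the cells.

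The cost is a sentence or two of SAP text and three degrees of freedom among about 450 participants (at most about 0.3% of the standard error if the cells are uninformative). If data were in hand, there is also a second set of estimates for five contrasts per outcome. Cell membership is known from the randomisation.

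### The SAP regression uses one row per participant per day, but its reported standard errors make no allowance for repeated days although treatment is randomised by participant

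*SAP*

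**What the plan says.** The SAP applies a single regression to all outcomes. The dependent variable "is each primary and secondary outcome for every participant" i on day d, so the unit of analysis is the participant-day. The primary outcome is repeated by definition: "the amount of sleep per participant during each 24-hour period, measured in hours".

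The other terms are all defined:

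- delta_i "is the baseline measure of the dependent variable for participant" i, so it is a baseline covariate and not a participant effect.
- phi_i holds gender and age.
- rho_d holds indicators for study day and for calendar date.
- epsilon_id is the only error term.

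The SAP's final paragraph says that each arm will be reported as the control mean plus the coefficient, together with "the standard error of each coefficient estimated by the regression".

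The Protocol (Treatment conditions) assigns both factors by person: it describes interventions on the home sleep environment and "attitudes towards sleep (randomized across individuals), and (2) a napping intervention (randomized across individuals"). Its Napping section also calls the nap assignment between-person.

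On frequency of measurement, the Protocol (Outcomes, A) plans a "psychomotor vigilance test (PC-PVT) on a daily basis". Cognitive function is measured "via a battery of laboratory tests conducted on a rotating basis" (Outcomes, B), and blood pressure is read several times (Outcomes, C).

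**The concern.** Each participant keeps one treatment assignment and contributes many rows. Information about an arm effect comes mainly from the number of people, and extra days from the same person add less than extra people would. A conventional regression standard error counts every row as a separate observation. It is valid here only if a person's days are uncorrelated once baseline, gender, age and day effects are in the model. Habitual sleep and reaction time differ between people, and a baseline mean captures those differences only with error, so some positive correlation should be expected to remain.

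This standard error is the only precision statistic in the plan, so the fault would pass straight into the reported results for all five arm effects on the primary outcome and on the PVT. Any interval built on it would be too narrow, and any test would reject too often. The rotating memory and inhibitory-control tests are affected less, as is blood pressure if it is read more than once after baseline. Outcomes with a single post-baseline value are not affected.

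**Working it through.** The plan gives no ICC, standard deviation, test level or power figure, so there is no stated number to reproduce.

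**Inputs from the documents.** The Protocol Overview describes "recruiting approximately 450 participants to work full-time for up to 28 business days in a data-entry job. After an eight-day baseline period", with six experimental groups in total.

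- Participants per group: 450 / 6 = 75.
- Post-baseline days: at most 28 − 8 = 20.
- Rows: up to 450 × 20 = 9,000 in all, or 75 × 20 = 1,500 per group, from 75 randomised people.

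**Assumptions.** The raw ICC r is varied from 0.05 to 0.6. The person effect is constant over the study (no drift). The baseline covariate is a mean of b = 8 days. The test is two-sided at 5%.

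**Formulas.** With total variance 1, the person-level variance left after adjusting for the baseline mean is r − r² / (r + (1 − r)/b). Dividing this by itself plus the within-person variance (1 − r) gives:

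- residual ICC = r / (1 + b·r)
- design effect = 1 + (m − 1) × residual ICC, with m post-baseline days
- true SE / conventional SE = √(design effect)
- rejection under no effect = 2 × (1 − Φ(1.96 / √(design effect)))

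For r = 0.4, b = 8, m = 20: residual ICC = 0.4 / 4.2 = 0.095; design effect = 1 + 19 × 0.095 = 2.81; SE ratio = 1.68; rejection = 24%.

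**Results for b = 8, m = 20**

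| Raw ICC | Residual ICC | Design effect | SE ratio | Rejection at nominal 5% |
|---|---|---|---|---|
| 0.05 | 0.036 | 1.68 | 1.30 | 13% |
| 0.2 | 0.077 | 2.46 | 1.57 | 21% |
| 0.4 | 0.095 | 2.81 | 1.68 | 24% |
| 0.6 | 0.103 | 2.97 | 1.72 | 26% |
| limit, r → 1 | 1/9 | 3.11 | 1.76 | 27% |

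The last row is a limit only when the person effect does not drift.

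**Other settings, r from 0.05 to 0.6**

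- Ten post-baseline days (b = 8, m = 10): SE ratio 1.15 to 1.39, rejection 9% to 16%.
- A rotating test with an assumed 2 baseline and 5 later values (b = 2, m = 5): SE ratio 1.09 to 1.45, rejection 7% to 18%.
- Drift or a noisier baseline can leave a larger residual ICC. At 0.20 with m = 20, the design effect is 1 + 19 × 0.20 = 4.80, the SE ratio 2.19 and rejection 37%.

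**Simulation of the SAP model under no effect.** Settings: 450 participants in six arms of 75; eight-day baseline mean, gender, age, study-day and calendar-date effects; entry staggered over 40 dates (assumed); 20 post-baseline days; 1,000 replicates per setting; first arm coefficient.

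| Raw ICC | Empirical SD / mean conventional SE | Rejection, conventional SE | Rejection, clustered by participant |
|---|---|---|---|
| 0.05 | 1.27 | 12.9% | 5.9% |
| 0.2 | 1.58 | 21.2% | 6.0% |
| 0.4 | 1.65 | 23.2% | 5.4% |
| 0.6 | 1.75 | 26.6% | 5.8% |

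With 10% of days missing at r = 0.4, the ratio was 1.62, and rejection was 22.9% with conventional and 5.5% with clustered standard errors.

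A separate, simpler simulation (600 runs, no calendar-date effects) gave conventional rejection of 16.4%, 22.2% and 24.8% at raw ICC 0.1, 0.3 and 0.5, against 5.3%, 5.4% and 5.4% with clustering. At ICC 0.5 the mean conventional SE was 0.0272, the true SD 0.0462 and the mean clustered SE 0.0460.

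**The case against.** **Silence is not a choice.** The SAP names no estimator or variance formula, and a participant-clustered standard error is also one that a regression can produce. On this view the plan is incomplete rather than wrong. It is true that the SAP never asserts independent errors. But every term in the model is defined, none represents the participant, and an analyst following the text would report the ordinary standard error. If clustering was intended, it must be written down.

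**No test is planned.** The SAP sets no significance level and plans no p-value or interval, so the rejection rates describe inference it does not specify. That is fair. The direct consequence is the SE ratio, and the rejection rates show what follows if a reader forms a test or interval.

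**The size rests on assumptions.** This also stands. The ICC is unknown, the SAP does not say that the baseline measure is an eight-day mean, 20 is a maximum count of working days, and nights of actigraphy may differ in number. The direction does not depend on these: any positive residual correlation makes the conventional standard error too small. Baseline adjustment is already credited in the figures, under an assumption favourable to the plan (no drift).

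**Incomplete text.** The text ahead of the SAP title was not available to this review. A variance statement there would answer the point.

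**Conclusion.** The concern holds and should be fixed before the results are relied on. As written, the plan understates the standard errors of all five arm effects on the primary outcome and on the daily PVT. Under the assumptions stated, the true standard error exceeds the reported one by about 30% to 72% with 20 post-baseline days, and by 15% to 39% with 10. The understatement could be larger if people drift after baseline or the baseline measure is noisier, and would vanish only if no within-person correlation remained. The coefficients themselves are not biased by this. Confidence in the direction is high; the exact size must await the ICC in the trial's own data.

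**What to change.** In the SAP's final paragraph, replace the clause on the standard error with wording such as: *and the standard error of each coefficient, which is cluster-robust, clustered by participant (the unit of randomisation)*. Leave the regression and its coefficients as planned. With about 450 clusters the method is dependable, and it brought rejection back to between 5% and 6% in the simulations.

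A participant random effect, or GEE with robust variance, would also address the correlation, but clustering changes least. An analysis of participant means could be added as a sensitivity analysis. It is not equivalent, because plain averaging drops the day-level study-day and calendar-date terms unless outcomes are adjusted for them first.

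The cost is one sentence and one software option, with no new data and no change to the point estimates. Reported standard errors for the repeated outcomes will become larger.
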